A Central Review Committee which composed by 2 separated subgroups. Subgroup 1 will be formed to confirm the type of events as defined by the device. If there are any discrepancies or disagreements in review, the Chairman will provide a final decision. The events that will be reviewed periodically include: appropriate shocks, inappropriate shocks, SVT, NSVT, PVC, ATP, Subgroup 2 will review SAE reports.

An Academic Committee composed by 11 members of certified electrophysiologists is formed to design and revise this study.

4 Rationale

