6.4 Treatment blinding

Treatment will be open to patients, investigator staff, persons performing the assessments, and the clinical trial team (CTT).

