8.5 External central review committee

A central review committee is responsible for periodic study endpoint events adjudication and SAE review in Rhythm Study. The central review committee is an independent group consisting of individuals who have experience and expertise in the management of trial participants within heart failure area and in the monitoring of ICD/CRT-D device. The review committee will be separated to two subgroups to perform device data adjudication and SAE review respectively.

Device data report will be exported timely into PDF version by doctors at baseline, 1 month, 3 months, 6 months, 9 months, 12 months when patient visits happen in local sites and all uncertain device events will be sent to the subgroup 1 for adjudication (Device Data adjudication Boards).

All aggregated SAE data will be provided to the subgroup 2 for review (Data and Safety Monitoring Boards, DSMB).

Then committee will have a meeting held by chairman either in the site or by conference call when necessary. Central review committee members will make every attempt to attend the meeting in person or by conference call. Total central review committee members will review and interpret device data (include VA events, ICD-shock, ATP, etc) and aggregated SAE data.

The central review committee members vote on all decisions. The member must be present in the meetings or must have given written recommendation to the chair prior to the meeting. Voting is by voice vote, but any members may request a secret written ballot. After decision making, the Chairman will provide minutes of the Board discussions to all Board members provide a summary (executive) report of each Board meeting to Novartis. A summary statement and recommendation from chairman will be provided in writing to the Novartis Medical Responsible within three working days of each meeting. The recipients will acknowledge receipt and provide a response, if necessary. If an urgent report (defines according to investigator discretion) is needed to interpret, at least 3 committee members should response and give their consensus decision to the investigator.

Committee Responsibility:

1. Endpoints adjudication use for final study

- 2. Provide clinical suggestion to investigators
- 3. Make amendment for protocol to NVS, for example patient exclusion and enrollment criteria

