12.4.1 Definition of primary endpoint

The endpoints of primary objective are as follow:

- 1. To explore the effect of ARNI in VA events, ICD shocks and ATP.
 - 1. Paired proportion of patients by the occurrence of at least one SVT over 6 months of ACEI/ARB and 6 months of ARNI treatment
 - 2. Paired proportion of patients by the occurrence of at least one NSVT over 6 months of ACEI/ARB and 6 months of ARNI treatment
 - 3. Paired proportion of patients by the occurrence of at least one PVC over 6 months of ACEI/ARB and 6 months of ARNI treatment
 - 4. Paired proportion of patients by the occurrence of at least one ICD shocks over 6 months of ACEI/ARB and 6 months of ARNI treatment
 - 5. Paired proportion of patients by the occurrence of at least one ATP over 6 months of ACEI/ARB and 6 months of ARNI treatment

The VA event, ICD shocks and ATP assessment will be captured by ICD or CRT-D implanted into the patients.

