12.8 Sample size calculation

12.8.1 Primary endpoint

McNemar Test is used in the primary analysis to test for 2 correlated proportions. Approximate formula from Machin et al (1997) is used to calculate the minimum size required.

For the proportion of discordant pairs, the following approximate formula is used:

Proportion Discordant =
$$P_t(1 - P_s) + P_s(1 - P_t)$$

where P_t and P_s are proportion of patients experiencing the event of interest during ACEI/ARB and ARNI treatment period respectively. Over here, both proportions are assumed to be similar to de Diego et al (2018)'s study. According to de Diego et al (2018)'s study, SVT (one of the VA event) has the following incidence 8/120 and 1/120 during ACEI/ARB and ARNI treatment period respectively. Hence, by substitute both into the equation above, proportion discordant calculated is 0.0739 after rounding off.

For the difference, a parameter under effect size is approximated by the following formula:

Effect Size =
$$P_t(1 - P_s) - P_s(1 - P_t)$$

and after substituting P_t and P_s defined above, the effect size calculated is -0.0583.

Thus, by considering the parameters defined above, power of 0.8 and significance level of 0.05, the sample size required is 175. Further consider a dropout rate of 20%, the minimum sample size required is 219.

The above calculation is calculated using PASS 11 software's Test for Two Correlated Proportion (McNemar Test) [Differences] procedure.

For proportion of patients had ICD or CRT-D shocks occurrence over 6 months of ACEI/ARB and 6 months of ARNI treatment, the above sample size will provide 95% - 98% power to detect a proportion difference of 0.075 at two-sided significance level of 0.05. The proportion difference is derived from the published literature (de Diego et al 2018).

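### Protocol sections 3 and 8.5 disagree on which device events subgroup 1 adjudicates, and no masking to treatment period is described; the risk falls mainly on SVT classification.

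*Protocol*

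**What the plan says.** Protocol section 3 (Study design) gives subgroup 1 a general remit: "Subgroup 1 will be formed to confirm the type of events as defined by the device". It then names six types: "The events that will be reviewed periodically include: appropriate shocks, inappropriate shocks, SVT, NSVT, PVC, ATP". Neither sentence is limited to doubtful events.

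Protocol section 8.5 describes how events reach subgroup 1. Doctors export the device report as a PDF at the scheduled visits, and then "all uncertain device events will be sent to the subgroup 1 for adjudication". The section does not say what makes an event uncertain, who decides, or whether anyone looks at the remainder. Two other sentences in 8.5 are broader. One says "Total central review committee members will review and interpret device data (include VA events, ICD-shock, ATP, etc) and aggregated SAE data". The other, in the list of responsibilities, reads "Endpoints adjudication use for final study". Meetings are held when needed, not on a fixed schedule.

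Section 6.4 leaves treatment open to patients, site staff, assessors and the trial team. All patients receive ACEI/ARB for six months and then ARNI for six months. No masking of the committee to visit, date or period is described.

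On data capture, section 12.4.1 says "The VA event, ICD shocks and ATP assessment will be captured by ICD or CRT-D implanted into the patients". SAP sections 4.1.1 and 7.4.1 define and test the primary endpoints without mentioning adjudication. They do not say whether the device, site or adjudicated label is analysed.

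**The concern.** Two sites could follow different rules and each point to protocol text that supports it: one refers every event, the other only those it finds doubtful. In this design the difference matters more than usual. Drug order is fixed, so anyone who knows when an event occurred knows the treatment. If doubtful events are selected or labelled differently in the second six months, the paired comparison absorbs that difference as a treatment effect.

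The exposed endpoint is SVT. Under protocol section 8.3.1 an episode qualifies by lasting at least 30 seconds or by causing haemodynamic disorder. The second limb can need clinical context beyond the device trace. The rhythm that triggered a shock or ATP can also need interpretation before it is counted as SVT. SVT is the event on which the sample size was set, and few patients decide that test.

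**Working it through.** **Inputs.** Protocol section 12.8.1: "SVT (one of the VA event) has the following incidence 8/120 and 1/120 during ACEI/ARB and ARNI treatment period respectively"; discordant proportion 0.0739; difference 0.0583 in size; power 0.80; alpha 0.05; 175 evaluable; 219 after 20% dropout. SAP section 7.1: two-sided tests. Protocol section 12.4.2: exact sign test if b + c < 25.

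**Step 1: reproduce the plan's figure.**
- Event on ACEI/ARB only: 8/120 x 119/120 = 0.0661.
- Event on ARNI only: 1/120 x 112/120 = 0.0078.
- Sum 0.0739; difference 0.0583. Both match.
- Power of the exact sign test, enumerated over the number of discordant pairs: 80.2% at N = 175 and 79.9% at N = 174, so 175 is the smallest adequate N.
- 175/0.80 = 218.75, rounded up to 219. Both sample sizes reproduce, and nothing in this point changes them.

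**Step 2: patients who decide the SVT test.**
- ACEI/ARB only: 175 x 0.0661 = 11.6.
- ARNI only: 175 x 0.0078 = 1.4.
- Together 175 x 0.0739 = 12.9, about 13. This is below 25, so the exact test applies.

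**Step 3: sensitivity to a few reclassified patients (assumed; the documents give no reclassification rate).** With c patients on one side and 1 on the other, and n = c + 1, two-sided P = 2 x (1 + n)/2^n.

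| ACEI/ARB only v ARNI only | P |
|---|---|
| 12 v 1 | 28/8192 = 0.003 |
| 11 v 1 | 26/4096 = 0.006 |
| 8 v 1 | 20/512 = 0.039 |
| 7 v 1 | 18/256 = 0.070 |

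From 11 v 1, four patients (4/11 = 36%) must move before significance is lost. From 12 v 1 it takes five (5/12 = 42%).

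**Step 4: false-positive rate if labels differ by period (assumed).** Take N = 175, equal true event rates in both periods, independence between periods, and all ACEI/ARB-period event patients kept. A share r of ARNI-period event patients is still counted as having an event. Two-sided rejection rate under the plan's test rule:

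| True rate | r = 1 | r = 0.9 | r = 0.8 | r = 0.7 |
|---|---|---|---|---|
| 6.7% (SVT planning rate) | 3.5% | 3.9% | 5.6% | 8.9% |
| 20% (assumed) | 4.9% | 7.5% | 16.1% | 31.8% |
| 40% (assumed) | 5.1% | 12.1% | 34.5% | 66.2% |

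The first row is the relevant one for SVT. The others show how the effect grows for a commoner event that depends on judgement in the same way.

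**Step 5: endpoints that are not exposed in this way.** Protocol 12.4.1 and SAP 7.4.1 count at least one shock and at least one ATP, with no restriction to appropriate therapy. Relabelling a shock as inappropriate leaves that patient's shock outcome unchanged. It matters only if the rhythm behind it then counts, or no longer counts, as SVT.

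**The case against.** The strongest reply is that the devices record the events, section 3 has the committee confirm type as the device defines it, and 8.5 calls the committee independent. Device capture does limit the risk, and the duration limb of SVT leaves little room for opinion. Independence is not masking, however, and the haemodynamic limb remains.

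Several stronger readings are tempting and are not supported:
- *Only doubtful events are ever adjudicated.* That is the only referral route described, but 8.5 also has members review device data generally. The text is unclear within 8.5 as well as against section 3; it is not plainly selective.
- *The site decides what is uncertain, and the exported report shows the date.* The workflow suggests the first. Neither is stated, and the report's content is not described.
- *Appropriate versus inappropriate labels bias the shock endpoint.* They do not, because any shock counts.
- *A handful of episodes would overturn the SVT result.* The endpoint is at least one event, so every qualifying first-period episode in each of about four patients would have to be reclassified, all in one direction. At the SVT planning rate, losing 20% of ARNI-period event patients moves the false-positive rate only from 3.5% to 5.6%. SVT is also one of five primary tests.
- *The added workload is small.* At planning rates about 15 (219 x 8/120 = 14.6) and 2 (219 x 1/120 = 1.8) patients have SVT in the two periods. Shock and ATP episodes come on top, and the documents do not count them.

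**Conclusion.** The inconsistency between sections 3 and 8.5 is in the current text, and the SAP does not resolve it. In an open-label comparison with fixed drug order, it leaves room for referral and SVT classification to differ by period. That is a plausible route to bias; the documents do not show that it has occurred.

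The size depends on assumption. The SVT test rests on about 13 discordant pairs, and moving four patients takes it from P=0.006 to P=0.070. A 20% or 30% loss of ARNI-period event patients at the SVT planning rate gives a false-positive rate of 5.6% or 8.9%, against 3.5% with no loss. This is a worthwhile low-cost improvement, not a flaw that invalidates the primary analysis.

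**What to change.** 1. Reconcile protocol sections 3 and 8.5 so that every SVT, shock and ATP episode goes to the existing subgroup 1, whether or not anyone thinks it uncertain. Include episodes where either limb of the SVT definition is in question, so that a short run with possible haemodynamic disorder is not left out.
2. Redact visit, date and treatment period from the device report and from any clinical notes sent with it.
3. Amend section 3 to say that NSVT and PVC are device-counted and not adjudicated. Otherwise its list would still conflict with 8.5.
4. State in the SAP that the adjudicated classification is analysed.

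If full review proves too heavy, a lesser option is to define uncertain, name who applies it, and audit a sample of unreferred events under the same masking.

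The cost is a protocol amendment with the required approvals, redaction work and more committee time. The documents do not give the shock and ATP episode count that would size it. Amendment 2 reports 142 patients enrolled by 31 January 2022, so earlier events would need review from the PDFs already exported. No new committee is needed, and 175 and 219 stand.

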8.6 Additional assessments

No additional tests will be performed on participants entered into this study.

8.6.1 Clinical outcome assessments

Not applicable.

8.6.1.1 Additional biomarker assessments

Not applicable.

9 Study discontinuation and completion

9.1 Discontinuation and completion

9.1.1 Study treatment discontinuation and study discontinuation

Discontinuation of study treatment for a patient occurs when study treatment is stopped earlier than the protocol planned duration, and can be initiated by either the patient or the investigator.

The investigator must discontinue study treatment for a given patient if, he/she believes that continuation would negatively impact the patient's well-being.

Discontinuation from study treatment is required under the following circumstances:

- 1. Patient/guardian decision
- 2. Pregnancy
- 3. Use of prohibited treatment as per recommendations in the prohibited treatment section
- 4. ACEI/ARBs daily dosage below guided dosage last for 1 month
- 5. Any situation in which study participation might result in a safety risk to the patient
- 6. Withdrawal of informed consent

Study treatment may be discontinued at the investigator's discretion if any of the following occurs:

- 1. Any severe, or suspected AE, that may jeopardize patient well-being, if the study drug is continued
- 2. Suspected occurrence of angioedema
- 3. Serum potassium >6.0 mmol/L at follow Visit
- 4. Any laboratory abnormalities that in the judgment of the investigator, taking into consideration the patient's overall status, prevents the patient from continuing participation in the study

If discontinuation of study treatment occurs, the Investigator should make a reasonable effort to understand the primary reason for the patient's premature discontinuation of study treatment and record this information.

Patients who discontinue study treatment or who decide they do not wish to participate in the study further should NOT be considered withdrawn from the study UNLESS they withdraw their consent (see withdraw of informed consent section). Where possible, they should return for the assessments indicated in the assessment schedule. If they fail to return for these assessments for unknown reasons, every effort (e.g. telephone, email, letter) should be made to contact the patient/pre-designated contact as specified in the lost to follow-up section. This contact should preferably be done according to the study visit schedule. Patients are to be discontinued from the study treatment if patient has not received the study treatment for > 14 days.

If the patient cannot or is unwilling to attend any visit(s), the site staff should maintain regular telephone contact with the patient, or with a person pre-designated by the patient. This telephone contact should preferably be done according to the study visit schedule.

After discontinuation from study treatment, at a minimum, in abbreviated visits, the following data should be collected at clinic visits or via telephone/email contact:

- New/concomitant treatments
- Adverse events/SAE

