5.2 Exclusion criteria

Participants meeting any of the following criteria are not eligible for inclusion in this study.

- 1. History of hypersensitivity to any of the study treatments or its excipients or to drugs of similar chemical classes.
- 2. Patient received target dose (≥200 mg/d) of ARNI for 2 weeks continuously within the 6-week period prior to study enrollment.
- 3. Participation in other clinical studies 3 months prior to participating study.
- 4. Advanced cancer or other significant comorbidities with life expectancy of <1 year.
- 5. Previous history of angioedema associated with ACEI/ARB treatment, hereditary or idiopathic angioedema.
- 6. Patients with renal artery stenosis history.
- 7. Current stage D HF patients requiring vasoactive drugs.
- 8. Symptomatic hypotension < 100/60 mmHg at visit 1 (screening) or Symptomatic hypotension < 90/60 mmHg in anti-hypertension drug treatment at visit 1 (screening).
- 9. Serum potassium >5.4 mmol/L at visit 1 (screening).
- 10. Estimated glomerular filtration rate (eGFR) < 30 mL/min/1.73m² as measured at visit 1 (screening).
- 11. Pregnant or nursing (lactating) women.
- 12. Other exclusion depend on investigator's discretion.

6 Treatment

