6.1.5 Treatment duration

The planned duration of treatment for ACEI/ARB and ARNI is 6 months each. During the ACEI/ARB period, the drug choice and dosage are at the discretion of the physician. The EOS will occur when the pre-specified number of patients completed the 12 months treatment. Patients may be discontinued earlier due to unacceptable toxicity and/or treatment is discontinued at the discretion of the investigator or the patient. For patients who in the opinion of the investigator are still deriving clinical benefit from ARNI, every effort will be made to continue provision of study treatment.

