6.2.2 Prohibited medication

Followed by ARNI instructive document. Concomitant use of ARNI with an ACEI/ARB is contraindicated because of the increased risk of angioedema.

Bile acid sequestrants (cholestyramine and colestipol) are also prohibited to avoid disturbing effect on the drug absorption of study medication.

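### ACEI/ARB angioedema bars entry, but once a patient is enrolled it is only a discretionary reason to stop, and the protocol does not say whether ARNI may still be started

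*Protocol*

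**What the plan says.** Protocol 5.2, exclusion 5, reads "Previous history of angioedema associated with ACEI/ARB treatment, hereditary or idiopathic angioedema". Section 6.2.2 states: "Concomitant use of ARNI with an ACEI/ARB is contraindicated because of the increased risk of angioedema".

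The planned sequence is 6 months of ACEI or ARB followed by 6 months of ARNI (6.1.5), with ARNI first dispensed at Visit 4 (6.7). On the first period, 6.1.5 says "During the ACEI/ARB period, the drug choice and dosage are at the discretion of the physician".

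Section 9.1.1 holds four relevant provisions:

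- A general duty: "The investigator must discontinue study treatment for a given patient if, he/she believes that continuation would negatively impact the patient's well-being".
- A required list of six items. It names pregnancy, prohibited treatment and one month of ACEI/ARB below the guided dose. Item 5 is broad: "Any situation in which study participation might result in a safety risk to the patient". Angioedema is not named.
- A second list that opens "Study treatment may be discontinued at the investigator's discretion if any of the following occurs". Its item 2 is "Suspected occurrence of angioedema".
- A time limit: "Patients are to be discontinued from the study treatment if patient has not received the study treatment for > 14 days".

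Section 6.5.2 (repeated in SAP 3.3.2) withdraws patients who meet a dose-limiting toxicity defined in the product label. In the glossary, study treatment includes the control drugs, and stopping it need not mean leaving the study. Neither document says whether a patient who had angioedema in the ACEI/ARB period may go on to ARNI.

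**The concern.** The first 6 months expose every patient to the drug classes named in exclusion 5. A patient can therefore acquire, on study, the history that would have kept them out, and do so shortly before receiving the drug for which 6.2.2 itself raises an angioedema risk. At that point the protocol moves from a bar to an option. Two sites could read the same event differently: one under the broad required item, the other under the item that names it and leaves the decision open.

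What is at stake is the safety of a small number of patients at first ARNI exposure. The point does not bear on the hypothesis test or the sample size.

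**Working it through.** The plan states no figure on this point, so the check is a comparison of its rules.

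**1. How entry exclusions carry over into the study**

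| Condition | At entry (5.2) | On study | Reason given for a discretionary rule |
|---|---|---|---|
| Pregnancy | Excluded | Required stop (9.1.1), with testing and a mandatory rule at Visit 4 (8.4.3) | Not applicable |
| Potassium | Excluded above 5.4 mmol/L | Discretionary above 6.0 mmol/L (6.2.3, 9.1.1) | Yes: transient hyperkalemia (Amendment 1 table) |
| eGFR | Excluded below 30 | Discretionary for a fall of more than 50% (8.4.1); a 50 mg bid ARNI starting dose is given for eGFR below 30 (Table 6-3) | Continuation is planned for through the dose table |
| ACEI/ARB angioedema | Excluded | Discretionary when suspected (9.1.1) | None found |

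Angioedema is the only one of these four with neither a mandatory rule nor anything in the text that explains the discretion.

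**2. Can a patient reach ARNI after angioedema without meeting a named bar?**

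- A patient develops angioedema on an ACEI in the first period.
- The investigator may stop study treatment but, under the item that names the event, need not.
- The physician chooses the drug in this period (6.1.5) and moves the patient to an ARB within 14 days. The 14-day rule is not triggered.
- If the ARB dose is adequate, the rule on one month below the guided dose is not triggered either.
- At Visit 4 the patient is on an ARB, so the 36-hour washout, which applies to ACEI only, is not needed. Table 8-1 marks the inclusion/exclusion check at screening only.
- ARNI is dispensed.

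Only the two general clauses of 9.1.1 and the label-based rule of 6.5.2 stand in the way. If ACEI/ARB is stopped instead, 9.1.1 still does not say whether ARNI may be started later.

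**3. Cost of a mandatory rule**

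A patient who never takes ARNI falls outside the SAP efficacy analysis set (SAP section 6, at least one ARNI dose), and the McNemar comparison uses complete pairs (protocol 12.4.4). Such a patient contributes no pair. As an illustration only, an assumed share of 0.1% to 2% of the 219 planned patients gives:

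- 219 × 0.001 = 0.2 patients
- 219 × 0.02 = 4.4 patients

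The plan's dropout allowance is 219 − 175 = 44 patients. These figures describe the cost of the change. They say nothing about the level of risk.

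**The case against.** The strongest reply has three parts.

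- **The two rules cover different things.** Exclusion 5 concerns an established history, while 9.1.1 concerns a suspicion. Leaving room for judgment over an unconfirmed swelling is defensible. This stands, and it is why the fix separates suspicion from confirmation. It does not supply the missing rule for a confirmed event.
- **Mandatory protection already exists.** Item 5 of the required list is triggered by anything that might put the patient at risk, which is a low bar, and the general duty to stop adds to it. This stands in part. Most investigators would probably use these clauses. They still rest on judgment, and they share a section with a specific item that makes the event discretionary.
- **The label may settle it through 6.5.2.** It may. The label is not among the documents, so whether it names angioedema, or bars ARNI after angioedema on another drug, cannot be seen here.

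The harm also needs several steps in a row: an event, a prompt change of drug, and an investigator who sees no risk. That supports a low severity.

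A reader might go further and infer that the potassium and eGFR entry limits should also be reapplied at Visit 4. The documents do not support that as a defect. Both values are scheduled at Visit 4. Section 8.4.1 says the Month 6 eGFR is there to guide the investigator, 6.2.1.1 asks the investigator to assess potassium, and 10.1.1 requires review of out-of-range results. Table 6-3 plans an ARNI start at eGFR below 30, and the discretionary potassium rule was a deliberate choice with a stated reason.

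**Conclusion.** The point holds for angioedema only. No rule by name bars ARNI after angioedema on an ACEI or ARB, the one rule that names angioedema is discretionary, and 9.1.1 does not address starting ARNI afterwards.

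It would be too strong to say that the protocol leaves these patients unprotected or directs that they receive ARNI. The general clauses and the label-based withdrawal apply to them, and the gap is one of clarity and consistency between rules.

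Severity is minor: a safety correction to the text. The number of patients affected cannot be derived from the documents. The conclusion assumes that the product label does not already close the gap through 6.5.2. If it does, the change only makes that explicit in the protocol.

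**What to change.** In 9.1.1, take angioedema out of the discretionary list and put it in the required list, so that the two lists no longer compete. Suggested wording: study treatment is interrupted for suspected angioedema and permanently discontinued if the event is confirmed or cannot be ruled out; a patient with such an event in the ACEI/ARB period must not start ARNI, consistent with exclusion 5.

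Because study treatment includes both periods, the same sentence covers angioedema on ARNI itself. The existing 14-day rule already limits how long an interruption can last before treatment must be discontinued. The potassium and eGFR rules stay as they are.

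The change needs one protocol sentence and no new assessments. Its downside is that some patients, probably few, would not switch and would be lost to the paired analysis. Patients who stop after starting ARNI remain in the SAP efficacy analysis set, and 9.1.1 already asks them to return for scheduled assessments where possible.
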